8.5 Primary objective analysis

An intention to treat analysis will be conducted of the primary outcomes for the study. Assuming that a descriptive comparison of the intervention to the control group does not demonstrate statistically significant differences in terms of demographics, vaccine drivers/barriers, or vaccine knowledge, we will report on the relative rate of influenza vaccination for the intervention group compared to the control group. This is given simply by:

RR = rate of influenza vaccination among intervention group rate of influenza vaccination among control group

We will also conduct logistic regression modeling of influenza vaccination as follows:

$$logit(Y) = \beta_0 + \beta_1 M + \sum_i \beta_i \alpha_i + \varepsilon$$

Where:

logit(Y) = ln(Y/1-Y) for the binary variable designation of influenza vaccination status M = the binary designation for Intervention (messaging) vs Control (no messaging) $\alpha_j = the$ baseline covariates measured in the study (e.g. demographics, vaccine drivers/barriers or knowledge) $\epsilon = the$ error term of the regression.

Vaccine drivers and barriers are described above in Section 8.1: Derived Variables

For the logistic regression model the p-values, odds ratio and associated 95% CI associated with each of the β parameter estimates will be reported.

Kaplan-Meier curves will be constructed for time-to-influenza vaccination, using the participant estimated dates of influenza vaccination from the 3 and 6 month surveys.

- 8.6 Secondary objective analysis
- 8.6.1 To examine predictors of vaccination status, including cardiovascular condition type, vaccine drivers/barriers, and vaccine knowledge, across and between CVD-I and CVD-C.

To examine predictors of vaccination status, including cardiovascular condition type, vaccine drivers/barriers, and vaccine knowledge, across CVD-I and CVD-C we will construct the model:

$$logit(Y) = \beta_0 + \sum_i \beta_i P_i + \sum_i \beta_i \alpha_i + \varepsilon$$

Where:

logit(Y) = ln(Y/1-Y) for the binary variable designation of influenza vaccination status P_i = the predictor of interest i (e.g. cardiovascular condition, vaccine drivers/barriers, vaccine knowledge) α_j = the baseline demographics ϵ = the error term of the regression.

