Cardiovascular condition type is described above in Section 8.1: Derived Data. Vaccine drivers and barriers are described above in Section 8.1: Derived Variables. The beta-parameter estimates, p-values, adjusted odds ratio and 95% CI will be reported. SHapley Additive exPlanations (SHAP) values will be used to assess the individual contributions of each predictor variable [Lundberg, 2017].

To describe the predictors of vaccination status and how it varies between CVD-I and CVD-C, we will use the model:

$$logit(Y) = \beta_0 + \beta_1 P + \beta_2 C + \sum_i \beta_i P_i * C + \sum_i \beta_i \alpha_i + \varepsilon$$

Where the variable *C* is a binary (1,0) designation for CVD-I and CVD-C respectively, and the beta-estimate for interaction term will be reported with the corresponding p-value, adjusted odds ratio and 95% CI. As with above, the SHAP values will be used to evaluate the individual contributions of each predictor variable.

People who report getting the influenza vaccination are asked a series of behavioral and attitudinal questions around where, how and when the vaccination was received. Those survey responses will be summarized for the study population. Similarly, people who did not obtain an influenza vaccine are asked a set of questions around attitudes and willingness to vaccinate, and those will also be summarized. Changes in response to questions on vaccine drivers and barriers will be examined between the baseline survey and the final survey.

8.6.2 To describe engagement with interventions, including clicking, opening, or completing the intervention messages

To examine differences in vaccination rates between individuals in the CVD-I group and its relationship to engagement with intervention messages, we will model:

$$logit(Y) = \beta_0 + \beta_1 M + \sum_i \beta_i \alpha_i + \varepsilon$$

Where:

logit(Y) = In(Y/1-Y) for the binary variable designation of influenza vaccination status M = the number of engaged messages (ordinal variable 0, 1, 2, 3, 4, 5, 6) α_i = the baseline covariates measured in the study (e.g. demographics, CVD type)

- 8.7 Exploratory objective analysis
- 8.7.1 To describe the self-reported impact of the COVID-19 pandemic on influenza vaccination behavior Descriptive summaries of the participant responses to the monthly survey questions on COVID-19 will be

provided.

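### SAP 8.6.1 prints the arm-by-predictor model with one main effect but an interaction for every predictor; fitted that way, a predictor's whole effect in CVD-I is reported as a difference between arms.

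*SAP*

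**What the plan says.** SAP 8.6.1 contains two models.

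- **Across arms.** The linear predictor contains "i \beta_i P_i + \sum_i \beta_i \alpha_i", so every predictor has a main effect. P_i is defined as "the predictor of interest i (e.g. cardiovascular condition, vaccine drivers/barriers, vaccine knowledge"), so i runs over different predictors. The covariates α in this section are "the baseline demographics" only.
- **Between arms.** The stated purpose is "To describe the predictors of vaccination status and how it varies between CVD-I and CVD-C". The linear predictor contains "\beta_1 P + \beta_2 C + \sum_i \beta_i P_i * C", plus covariates. The arm variable C "is a binary (1,0) designation for CVD-I and CVD-C respectively". The reported result is the interaction coefficient: "the beta-estimate for interaction term will be reported with the corresponding p-value, adjusted odds ratio and 95% CI". SHAP values are to be used here too, as for the first model.

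The SAP does not define P without an index, and does not say that P stands for the full set of predictors.

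**The concern.** An interaction coefficient measures a difference between arms only if the predictor also has its own main effect. As printed, at most one predictor has one. The demographics-only covariates do not supply the others.

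Predictors across and between the arms are a named secondary endpoint. If ordinary predictors of vaccination, such as being offered the vaccine by a provider, are presented as acting differently in the two arms, readers will take them as identifying who benefits from the messages. The data would not have shown that.

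**Working it through.** **1. What the coefficient estimates.** Take a predictor P_k with no main effect of its own, and write g_k for its interaction coefficient.

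- In CVD-C, C = 0, so g_k × P_k × C = 0. The effect of P_k is fixed at zero.
- In CVD-I, C = 1, so the term is g_k × P_k. The effect of P_k is g_k.

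So g_k is the whole log OR of P_k in CVD-I. With a main effect b_k, the effects are b_k in CVD-C and b_k + g_k in CVD-I, and g_k is the difference that the SAP wants.

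**2. Inputs from the documents.**

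- Two-sided 5% level (SAP 8.1) and 1:1 allocation (SAP 4).
- Planned size: for 50% against 53%, the arcsine formula gives 4,355.3 per arm, and 2 × 4,355.3 = 8,710.6, against 8,710 in the SAP table. The SAP text rounds the requirement to about 8,000, and 49,000 × 0.16 = 7,840.
- Low-response case: SAP 4 cites a completion rate of about 7%, and 49,000 × 0.07 = 3,430.

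**3. Assumptions, not in the documents.** Four independent binary predictors, each with the same OR in both arms (no true interaction); ORs of 1.0, 1.2, 1.5 and 2.0; prevalence of 10%, 30% and 50%; vaccination of about 50% in CVD-C and 53% in CVD-I.

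**4. Simulation, 300 trials per scenario.** The model as printed (main effect for the first predictor only) is compared with the complete model. The result is for the second predictor's interaction. Percentages are trials significant at 5%, for prevalence 10 / 30 / 50%.

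| Analysed | Common OR | As printed: mean interaction OR | As printed: significant | Complete: mean OR | Complete: significant |
|---|---|---|---|---|---|
| 8,000 | 1.0 | 1.00 | 6 / 5 / 4% | 0.99–1.00 | 6 / 6 / 2% |
| 8,000 | 1.2 | 1.19–1.20 | 37 / 70 / 83% | 1.00 | 3 / 5 / 4% |
| 8,000 | 1.5 | 1.49–1.50 | 96 / 100 / 100% | 0.99–1.00 | 6 / 5 / 5% |
| 8,000 | 2.0 | 1.99–2.01 | 100 / 100 / 100% | 0.99–1.01 | 7 / 5 / 6% |
| 3,430 | 1.2 | 1.19–1.22 | 20 / 39 / 47% | 0.98–1.01 | 6 / 4 / 4% |
| 3,430 | 1.5 | 1.50 | 70 / 96 / 99% | 0.99–1.01 | 7 / 5 / 4% |

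The first predictor, which keeps its main effect, is significant in 3–9% of trials under the printed model. A separate simulation at 8,000, with prevalence 10–40%, gave 36–78% at a common OR of 1.2 and 96–100% at 1.5, against 4–8% with full main effects.

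**5. Hand check.** Only CVD-I informs g_k, so SE ≈ 1/√(n × 0.25 × q(1 − q)), with n = 4,000 and prevalence q.

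- q = 0.4: SE = 1/√(4,000 × 0.25 × 0.24) = 0.0645. For OR 1.2, z = 0.1823/0.0645 = 2.82, which is significant in about 81% of trials.
- q = 0.1: SE = 1/√(4,000 × 0.25 × 0.09) = 0.1054. For OR 1.2, z = 1.73, about 41%. For OR 1.5, z = 0.4055/0.1054 = 3.85, about 97%.

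These agree with the simulations to within a few percentage points.

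**The case against.** **It is probably a notation slip.** The formula cannot be taken wholly literally. The same β_i serves both interactions and covariates, and the covariates are summed over i although defined with index j. The protocol's predictor models use a single P, so the lone P looks like a carry-over. The protocol's COVID-19 interaction model gives both interacting variables a main effect, which suggests that the team knows the convention. If P is shorthand for all P_i, or if one predictor is fitted at a time with P, C and their product, there is no bias. This stands as a reason for moderation. It does not remove the point: the SAP states neither reading, and its definition of P_i and the preceding model point the other way.

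**Stronger readings that the documents do not support.**

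- A reader might infer that every real predictor will be declared different between arms. The estimate is always shifted to the full predictor OR, but significance is near certain only at an OR of about 1.5 or more with about 8,000 analysed.
- A reader might infer that fitting one predictor at a time also fails, because one coefficient cannot carry a seven-category condition type. That requires coding the categories as one number while expanding the interaction by level, and the SAP does not state such coding.
- A reader might add a multiplicity objection, since SAP 7.1 implies about 21 interaction coefficients (6 + 10 + 5). That would apply to a correct model too. The SAP promises estimates, p-values and intervals, not a decision rule for each coefficient.
- A reader might infer that no other between-arm information is planned. The protocol also has predictor models within each arm (8.2.3), and SAP 6 does not list them as dropped.

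**Conclusion.** The point holds for the formula as printed and should be fixed. For any predictor without its own main effect, the model cannot answer its stated question: it reports the effect in CVD-I in place of the difference between arms. The shift in the estimate follows from the algebra whatever the sample size. How often it produces a false significant result depends on the assumed predictor strength and prevalence. With 8,000 analysed and prevalence 10–40%, it is roughly 36–78% at a common OR of 1.2 and 96–100% at 1.5. With 3,430 analysed and prevalence 10–50%, it is 20–47% and 70–99%.

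Predictors with no effect and the one entered as P are not materially affected. The primary comparison uses a different model and is untouched. Because this is a secondary analysis and the formula may only be loosely written, the documents do not support treating it as a flaw in the trial's main conclusion.

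**What to change.** Replace the between-arm formula in SAP 8.6.1 with

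logit P(Y = 1) = b0 + Σ_i b_i P_i + b_C C + Σ_i g_i (P_i × C) + Σ_j d_j α_j

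Use separate symbols for main effects (b), interactions (g) and covariates (d). Add one sentence saying that each categorical predictor enters as indicator variables in both the main-effect and the interaction parts. If one predictor at a time is intended, say so and drop the sums over i.

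A joint test for each multi-level predictor, covering all its interaction terms, would be a reasonable addition but is optional.

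The cost is one formula and one sentence before the analysis is run. No new data are needed, and neither the sample size nor the primary analysis changes.

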7.1 Derived Data

Cardiovascular condition type will be one of the following for the purposes of the secondary analysis objectives:

- People with self-reported arrhythmia only (not including atrial fibrillation)
- People with self-reported atrial fibrillation only
- People with self-reported heart attack, cardiac arrest or coronary artery disease only
- People with self-reported congestive heart failure only
- People with self reported stroke only
- People with two or more of the above conditions
- People with other cardiovascular conditions

Vaccine drivers and barriers of interest include:

- Number of visits to a primary care provider in the 3 months prior (categorized as None, 1-2, 3 or more)
- Number of visits to a cardiology specialist in the 3 months prior (categorized as None, 1-2, 3 or more)
- Hospitalization in the 3 months prior (categorized as none, once, 2 or more)
- Offered influenza vaccination by a healthcare provider (categorized as Yes, No, Unsure)
- Healthcare provider informed individual they were in a 'high risk group' (categorized as Yes, No, Unsure)

Vaccine knowledge factors are based on responses to the survey question "What sources of information do you use to learn about the flu vaccine?", with possible responses:

- Healthcare Professionals
- Family member or peers
- Social media including blog posts
- Mobile applications
- Conventional news media (e.g. television, newspapers)

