8 STATISTICAL METHODS

8.1 General Statistical Approaches

For the study variables, we will perform distributional analysis. When describing the study population, we will use min, max, mean, and standard deviations for continuous variables (i.e. age, BMI) and frequency counts for categorical variables (i.e. gender, ethnicity). For both continuous and categorical variables, we will report on the number of participants evaluated for that variable, as well as the number of people with non-missing values. For the study variables, we will also look at individual-level rates of missing data. Missing data or unknown responses will be described separately and not be counted in the summary descriptions of the variables. We will report on the percent of missing data for each of the included data sources (surveys, activity data) and evaluate whether any missingness is associated with baseline participant-level characteristics in the case of missing survey data or with the outcome in the case of activity tracker data.

Statistical testing comparing variables will be performed at the 5% significance level using two-sided tests or two-sided 95% confidence intervals (CI), unless otherwise specified. Comparison of means will use Student's t-test for normal distributions, or a Mann-Whitney U test for non-normal distributions. Comparisons of frequencies will use chi-square tests. Regression modeling approaches are described below. We will report on the size of the beta-parameter estimate and the associated significance level (p-value) for each predictor variable.

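### The secondary arm-by-predictor interaction model is read coefficient by coefficient, with no joint test per predictor and no stated reference level

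*SAP*

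**What the plan says.** The second model in SAP 8.6.1 is introduced with the words "To describe the predictors of vaccination status and how it varies between CVD-I and CVD-C, we will use the model". It contains arm, the predictors, a sum of predictor-by-arm products and baseline demographics. On reporting, the SAP says that "the beta-estimate for interaction term will be reported with the corresponding p-value, adjusted odds ratio and 95% CI". It adds SHAP values for each predictor's contribution, but these are not a test.

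The general rules are in SAP 8.1. Tests are "performed at the 5% significance level using two-sided tests or two-sided 95% confidence intervals (CI), unless otherwise specified", and for regression models: "We will report on the size of the beta-parameter estimate and the associated significance level (p-value) for each predictor variable". Nothing different is specified for the interaction model.

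SAP 7.1 defines the predictors:

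- Condition type: "Cardiovascular condition type will be one of the following for the purposes of the secondary analysis objectives". Seven classes follow, the last being "People with other cardiovascular conditions".
- Five drivers and barriers with three levels each, for example "Number of visits to a primary care provider in the 3 months prior (categorized as None, 1-2, 3 or more".
- Vaccine knowledge: five possible information sources.

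No reference level is named for any of them. The only multiplicity rule in either document is the Benjamini-Hochberg correction in protocol 8.2.4. It covers the protocol's exploratory between-group comparisons, and the SAP does not carry it over.

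**The concern.** The objective is stated at the level of the predictor: does condition type, or contact with healthcare, relate to vaccination differently in the two arms? The planned output is at the level of the coefficient. For a factor with several levels, each interaction coefficient contrasts one level with whichever level is the reference. None of these contrasts tests the factor as a whole, and a different reference gives different contrasts with different p-values. With the reference unstated, that choice remains open after the data are seen.

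The number of coefficients adds to this. About 20 p-values at 5% with no true interaction produce about one below 0.05 on average. A small p-value beside one cardiac condition could easily be taken as a sign that the messages work better or worse in that condition, and could influence how later campaigns are targeted.

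**Working it through.** The documents give no error rate for this model, so there is no figure of the plan's to reproduce for the claim itself. The simulations use about 8,000 respondents and 1:1 arms, both from SAP section 4. The table there does reproduce: for 50% versus 53% the arcsine formula gives 4,355 per arm, and 2 × 4,355 = 8,710, as tabulated.

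**Step 1. Count the interaction coefficients (SAP 7.1).**

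| Predictor | Levels | Coefficients |
|---|---|---|
| Condition type | 7 (6 if the residual class is empty) | 6 (or 5) |
| Five drivers/barriers | 3 each | 5 × 2 = 10 |
| Information sources | 5 | 5 if multi-select (4 if single choice) |
| Total | | 6 + 10 + 5 = 21; lowest 5 + 10 + 4 = 19 |

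The SAP does not state this total. The residual class may be empty because eligibility requires one of the listed conditions. The SAP does not say whether the knowledge question is multi-select.

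**Step 2. Independent tests, no true interaction.** P(at least one p<0.05) = 1 − 0.95^k.

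- k = 21: 1 − 0.95^21 = 65.9%; expected number 21 × 0.05 = 1.05
- k = 20: 64.2%
- k = 19: 62.3%
- The figure passes one half at k = 14 (51.2%; k = 13 gives 48.7%)

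**Step 3. Allow for correlation.** Coefficients that share a reference level are correlated, so the full logistic model was simulated with 8,000 respondents, main effects present and all interactions zero. Level shares had to be assumed. There were 1,500 trials per scenario.

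- 21 coefficients: 58-65% across three scenarios
- 20 coefficients: 62-68% across two scenarios
- 19 coefficients, single-choice knowledge item and small reference classes: 51% (Monte Carlo error about 1.3 points)

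Two further sets of 1,000 trials with 21 coefficients and other assumed shares gave 65.5% and 65.7%. The per-coefficient range is therefore about 51-68%.

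**Step 4. One p-value per variable.** This reading gives 7 tests with a single knowledge item (1 + 5 + 1) or 11 with five sources (1 + 5 + 5).

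- Independent: 1 − 0.95^7 = 30.2%; 1 − 0.95^11 = 43.1%
- Simulated: 32-46%

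**Step 5. Condition type alone.** In the two 1,000-trial sets, at least one of the six condition coefficients had p<0.05 in 24.8% and 25.6% of null trials. The joint test of condition by arm rejected in 5.3% and 5.7%.

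**Step 6. Dependence on the reference.** In 400 null trials, each of the seven classes was used as reference in turn. In 43% of trials, whether any condition-by-arm coefficient reached p<0.05 depended on that choice. The joint test is the same for every reference.

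**Step 7. Effect of the remedy.** Joint tests per predictor answer the right question, but without adjustment they still leave the 30-46% of step 4. With Benjamini-Hochberg over the 11 factor-level tests, any false claim occurred in 5.0% and 5.4% of null trials.

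**The case against.** The strongest reply is that the plan contains no rule that turns a single p-value into a claim. The model is introduced as description, and SAP 8.6.1 promises only to report estimates, p-values, odds ratios and intervals. Reporting unadjusted p-values in a descriptive secondary model is common, and whether to adjust them is partly a matter of judgement. This stands. A reader might infer that the plan commits the sponsor to a probable false claim, but the documents do not support that. What remains is that a p-value per coefficient at 5% is prespecified under a listed secondary objective, and it is not a p-value for the question asked.

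Second, the SAP settles neither the count nor the reading. Predictors are introduced only by example. The reporting sentence speaks of the interaction term in the singular, and SAP 8.1 promises an "associated significance level (p-value) for each predictor variable". The equation pairs one main-effect term with a sum of interactions. If one p-value per variable is meant, the chance falls below one half. The per-coefficient reading is the more natural one, because the p-value is tied to a beta estimate and a multi-level factor has no single beta. Even so, it would be wrong to state as certain that a spurious finding is more likely than not.

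Third, a reader might treat these interactions as randomised subgroup tests of the messages. The SAP does not present them so. The stated aim concerns predictors of vaccination across and between arms. The population is respondents to the 3- or 6-month survey (P1, SAP 8.2), and the drivers come from surveys offered after randomisation. It is an association analysis among respondents.

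**Conclusion.** The concern holds in a limited form. As written, the plan yields level-versus-reference p-values where the objective needs one test per predictor, and the reference is unstated. That defect does not depend on any view about multiplicity in secondary analyses.

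The 51-68% figure (or 30-46% with one p-value per variable) assumes that every interaction is zero, that all SAP 7.1 predictors enter one model, and that level shares are as simulated. With some real interactions, the number of true nulls falls and so does the chance; independent tests need at least 14 true nulls to exceed one half. The lowest per-coefficient scenario is barely above one half.

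Nothing here touches the primary comparison. It is a worthwhile, inexpensive improvement to a secondary analysis.

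**What to change.** In SAP 8.6.1:

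- State that each predictor's interaction with arm is tested by one likelihood-ratio or Wald test over all its levels.
- Present level-specific odds ratios with 95% confidence intervals as descriptive, with the reference level named and no claims drawn from single-coefficient p-values.
- Preferably, apply Benjamini-Hochberg across the factor-level tests (11 if the information sources are multi-select, 7 if single choice). Say that it controls the false discovery rate, and that it controls the chance of any false claim only when every null is true. This part is more debatable than the joint test, but the protocol already accepts the method for its exploratory comparisons.

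The cost is a sentence or two and standard software output, with no new data. The downside is fewer nominally significant secondary results.
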